#### 4.10 Exploratory Analysis

Time to Chemotherapy (TTC) is defined as the number of days from randomization to initiation of chemotherapy and will be summarized by treatment group descriptively for the subjects who receive chemotherapy as first systemic anticancer therapy after treatment discontinuation.

Listings will be provided for tumor biopsies obtained at pre-treatment, on-treatment and post-treatment periods.

Biomarker analyses may be conducted when study is closed.

#### 4.11 Independent Data Monitoring Committee

An independent IDMC external to both the Sponsor and clinical research organization CRO will be responsible for ongoing monitoring of the safety and efficacy according to the IDMC Charter. The IDMC will meet on a regular basis and will make recommendations as to whether the trial should continue, be amended, or be discontinued based on ongoing reviews of safety and efficacy data. IDMC responsibilities and review schedules are outlined in an IDMC charter.

#### 4.12 Safety Analyses

Unless otherwise specified, safety analyses will be conducted using the Safety population for ESR1-mut subjects and all subjects (ESR1-mut and ESR1- mut-nd). Safety evaluations will be based on the incidence, relationship, severity grade, and seriousness of treatment emergent adverse events (TEAEs), ECOG performance status, vital signs, ECGs, and laboratory tests of chemistry, hematology, and coagulation parameters, as well as dose modifications (interruptions/reductions) due to TEAEs, and treatment discontinuations due to TEAEs. In addition, study drug exposure and usage of concomitant medications will be summarized.

##### 4.12.1 Treatment Exposure

Treatment exposure will be summarized descriptively by treatment group and SOC type (fulvestrant vs AIs) as duration on treatment and extent of exposure to study drug.

**Duration on Treatment** will be defined as follows:

Treatment duration (days) for elacestrant and AIs will be calculated as (Last dose date – First dose date + 1).

Sponsor:	Radius		
Protocol:	RAD1901-308		
Document Version No.:	1.1 (Final)	Document Date:	10-MAY-2021

Treatment duration (days) for fulvestrant will be calculated as (End date of last cycle – First dose date + 1). End date of last cycle is the earliest of the following dates: the expected end date of last cycle, date of death, date of last known alive, date of subject withdrawal from the study, or the analysis cut-off date if subject is known to be alive after analysis cut-off date. Expected end date of last fulvestrant cycle is calculated as:

- x If last dose of fulvestrant was administered in cycle 1, expected end date of last cycle is the last dose date + 13 days
- x If last dose of fulvestrant was administered beyond cycle 1, expected end date of last cycle is the last dose date + 27 days

Measures of extent of exposure include the Total Number of Doses per Subject, Absolute Dose Intensity, Relative Dose Intensity (%) and compliance (%).

Duration on Treatment, Total Number of Doses, Absolute Dose Intensity, Relative Dose Intensity and Compliance will be summarized by treatment and SOC type (fulvestrant vs AIs), as well as presented in a by-subject data listing.

#### 4.12.1.1 Elacestrant/AIs

For subjects assigned to take the oral drugs of elacestrant and the AIs, the study drug is to be taken every day during treatment. The start and stop date will be recorded for each un-interrupted dosing period, where the same dose is taken every day. In case of a dose change, such as dose level change, or missing doses, etc, a new period will be recorded.

The number of doses in a period is the number of days in the period calculated as (end date – start date + 1), assuming one dose per day. The **Total Number of Doses** is then calculated by taking the sum of the number of doses in all the periods. Study drug **Compliance** is defined as *Total Number of Doses divided by Duration on Treatment*.

The dose intensity of a period is the sum of doses in the period divided by the number of days in the period calculated as (end date – start date + 1), assuming one dose per day. The **'Absolute Dose Intensity (mg/day)'** is then calculated by taking the sum of doses in all the periods divided by the sum of the number of days in each period. The **'Planned dose intensity (mg/day)'** for a subject is their initial dose. The **'Relative Dose Intensity (%)'** is Absolute Dose Intensity divided by planned dose intensity \*100.

#### Dose Reductions

Frequency tables on number of subjects with at least 1 dose reduction of any study drug will be provided.

Dose reductions due to AE for subjects receiving elacestrant will be summarized as follows:

Sponsor:	Radius		
Protocol:	RAD1901-308		
Document Version No.:	1.1 (Final)	Document Date:	10-MAY-2021

Number of subjects with at least 1 dose reduction

Time to first dose reduction

Number of dose reductions (0 vs 1 vs 2)

A listing with visit (cycle) dates, drug administration start and end dates and times, and end of study status will be provided. Subjects with missing or delayed doses will be listed.

#### 4.12.1.2 Fulvestrant

For subjects assigned to take fulvestrant, the study drug is to be taken via intramuscular injection on Days 1, 15, 29, and every 28 days thereafter.

For these subjects, the **Total Number of Doses** is derived by taking the sum of the number of doses recorded during treatment.

*Total Number of Intended Dose = 1, if Duration of treatment < 15*

*= 2, if 15 ≤ Duration of treatment < 29*

*= round ((Duration of Treatment - 28) / 28, 1) + 2*

**Compliance** is defined as *Total Number of Doses* divided by the *Total Number of Intended Doses*.

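### The fulvestrant intended-dose formula is one dose short when cycle 2 or a later cycle is cut off within its first 13 days, so compliance can read up to 150%

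*SAP*

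**What the plan says.** SAP 4.12.1.2 states the schedule: "the study drug is to be taken via intramuscular injection on Days 1, 15, 29, and every 28 days thereafter". The intended number of doses has three branches: 1 for a duration below 15 days; "2, if 15 ≤ Duration of treatment < 29"; and otherwise "round ((Duration of Treatment - 28) / 28, 1) + 2". The number of doses given is "derived by taking the sum of the number of doses recorded during treatment", and compliance is doses given over doses intended. No cap at 100% is stated.

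Duration is defined in SAP 4.12.1 as the end date of the last cycle minus the first dose date, plus 1. The cycle end need not be the planned one: "End date of last cycle is the earliest of the following dates: the expected end date of last cycle, date of death", with last-known-alive date and study withdrawal also in the list, "or the analysis cut-off date if subject is known to be alive after analysis cut-off date". The expected end is the last dose date plus 13 days if that dose was in cycle 1, and plus 27 days if it was later.

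Compliance is to be summarized by treatment and by type of standard-of-care drug, and listed by subject.

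**The concern.** The first two branches step up on the day a dose is due: the count becomes 2 on Day 15. The third branch does not. A third dose is due on Day 29, but rounding to the nearest whole cycle leaves the count at 2 until Day 42, and the same lag recurs in each later cycle. Because duration can stop mid-cycle, a subject can receive the day 1 injection, be truncated soon after, and have that injection counted as given but not as intended.

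At stake is the accuracy of one exposure measure for fulvestrant, which is the option that Protocol 9.1.1.2 steers fulvestrant-naive control subjects towards. Values above 100% for an injection given in clinic would draw queries, and an inflated ratio can conceal a missed injection. SAP 4.12.1.2 gives no fulvestrant dose-intensity formula, so compliance is the only exposure ratio it defines for this drug.

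**Working it through.** The plan states no compliance figure, so there is none to reproduce. The check compares the formula with the doses due on or before day D, where D is duration in days.

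**Inputs.** Doses due on Days 1, 15, 29, 57, 85, 113, … (SAP 4.12.1.2). Intended doses from the three branches (SAP 4.12.1.2). Truncation rule and expected cycle end (SAP 4.12.1). Software SAS 9.4 (SAP 4.2.2), in which a second argument of 1 means rounding to the nearest integer.

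**Step 1: complete cycles, on schedule.**
- D = 56: (56 − 28)/28 = 1, intended 3, due 3.
- D = 84: (84 − 28)/28 = 2, intended 4, due 4.
- D = 112: (112 − 28)/28 = 3, intended 5, due 5.

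The formula is correct here.

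**Step 2: last cycle cut short, all due doses given.**

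| D (days) | (D − 28)/28 | Rounded | Intended | Given | Compliance |
|---|---|---|---|---|---|
| 29–41 | 0.04–0.46 | 0 | 2 | 3 | 150% |
| 42–55 | 0.50–0.96 | 1 | 3 | 3 | 100% |
| 57–69 | 1.04–1.46 | 1 | 3 | 4 | 133% |
| 70–83 | 1.50–1.96 | 2 | 4 | 4 | 100% |
| 85–97 | 2.04–2.46 | 2 | 4 | 5 | 125% |
| 113–125 | 3.04–3.46 | 3 | 5 | 6 | 120% |

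The shortfall is always one dose, on days 1–13 of each 28-day cycle from cycle 2, and its relative size falls with time on treatment. On the nominal schedule, checked for D up to 399, there is no over-count and the maximum is 150%.

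Example: doses on Days 1, 15 and 29, death on Day 35. D = 35, 7/28 = 0.25 rounds to 0, intended 2, given 3, compliance 150%.

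**Step 3: the other reading of the rounding argument.** If the 1 meant one decimal place, D = 29 would still give 3/2.0 = 150%, and D = 35 would give 3/2.3 = 130%. That reading does not remove the error.

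**Step 4: masking a missed dose.** Doses on Days 1 and 29, Day 15 missed, truncation at Day 40: 12/28 = 0.43 rounds to 0, so intended 2, given 2, compliance 100%. Three doses were due, so the correct value is 2/3 = 67%.

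**Step 5: would a ceiling repair it?** Replacing the rounding by ceil((D − 28)/28) + 2 matches the schedule on every nominal day. Protocol section 8 allows ±2 days on visits, however, and a late dose carries into D:
- Last dose Day 30 or 31, complete cycle: D = 57 or 58, ceiling 2, intended 4, compliance 3/4 = 75%. Current formula: 3/3 = 100%.
- Last dose Day 16 or 17 (the C1D15 dose): D = 29 or 30, ceiling 1, intended 3, compliance 2/3 = 67%. Current formula: 2/2 = 100%.

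**The case against.** The strongest defence is that rounding to the nearest cycle has a purpose: it absorbs the drift that visit windows and permitted dosing delays (Protocol 10.1.5.2.1) put into duration. Step 5 bears this out. The obvious replacement, a bare ceiling, would trade an error confined to early-truncated cycles for one that falsely lowers compliance in complete cycles. That stands, and it decides the form of the fix. It does not make the present count right for a cycle cut in its first 13 days.

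The defence is also right to limit the reach. A reader might infer four things that the documents do not support:

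- That the formula works only when the last cycle is complete. It is also correct for cycles cut on day 14 or later.
- That every fulvestrant subject still on treatment at the data cut-off is miscounted. Such subjects are generally truncated, but only those in the first 13 days of cycle 2 or later lose a dose.
- That any missed injection is hidden. If the Day 29 dose is the one missed, the last dose is in cycle 1, duration ends at Day 15 + 13 = Day 28, and compliance is 2/2 with or without the defect. The masking in step 4 needs Day 15 missed, Day 29 given and early truncation.
- That control-arm exposure as a whole is misreported. Aromatase inhibitor compliance follows a different rule (SAP 4.12.1.1), and total doses and duration do not use this denominator.

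The by-subject listing, the summary of reasons for withheld or delayed doses (Protocol 11.3.4) and the count of doses missed because of COVID-19 (SAP 4.12.1.2) offer partial safeguards. None of them corrects the percentage.

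**Conclusion.** Wrong as written, and minor. A stated rule gives a wrong result under the SAP's own definition of duration: one intended dose too few when cycle 2 or later is cut within its first 13 days. The overstatement is largest in cycle 2 (150%) and shrinks after that (133%, 125%, 120%). These figures assume nominal dosing days and all due doses given.

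How many subjects are affected cannot be known from the documents. It could be none or all of those truncated in cycle 2 or later. If subjects on treatment at the cut-off were spread evenly over the 28 days of a cycle, which is an assumption, 13/28 = 46% of those in cycle 2 or later would be miscounted.

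The consequence stays within a descriptive safety-section summary. No PFS or OS analysis uses compliance.

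**What to change.** Replace the three branches in SAP 4.12.1.2 with a count based on the visit of the last dose given: 1 intended dose if that visit was C1D1, 2 if it was C1D15, and cycle number + 1 if it was in cycle 2 or later.

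This resolves each case above. Doses on Days 1, 15 and 29 with death on Day 35 give 3/3 = 100%. Doses on Days 1 and 29 with truncation at Day 40 give 2/3 = 67%. A last dose on Day 31 with a complete cycle stays at 3/3 = 100%, and one on Day 17 stays at 2/2 = 100%.

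The SAP should add that the cycle number is the one recorded for that dose, so that a delayed dose is handled consistently.

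The cost is a one-line SAP change and the matching line of code. No new data are needed, because SAP 4.12.1 already uses the cycle of the last dose to set the expected cycle end.

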#### Dose Reductions

Dose reductions due to AE for subjects receiving fulvestrant will be summarized as follows:

Number of subjects with 1 dose reduction

Time to first dose reduction

Number of missing doses due to COVID-19 will be summarized using descriptive statistics.

Administration details due to COVID-19 will be presented in a by-subject listing.

#### 4.12.2 Adverse Events

All AEs will be coded to preferred term (PT) and system organ class and using the MedDRA (version 23.0) coding dictionary.

Analyses of AEs will be performed for those events that are considered to be treatment-emergent adverse events (TEAEs), where TEAE is defined as:

- x Any AE that was absent (i.e., had not occurred) or had resolved prior to the start of study drug, and which occurred on or after the date of the first dose of study drug and within 30 days of the last dose of study drug; or
- x Any AE that started prior to the first dose of study drug, was ongoing after treatment started, and increased in severity after the start of study drug and within 30 days of the last dose of study drug

Sponsor:	Radius		
Protocol:	RAD1901-308		
Document Version No.:	1.1 (Final)	Document Date:	10-MAY-2021

Adverse events will be summarized by subject incidence rates; therefore, in any tabulation, a subject contributes only once to the count for a given system organ class or PT. Preferred terms for a similar medical concept (i.e., synonym terms) will be grouped across different system organ classes in all AE summary tables except as otherwise noted. All listings will present PTs by original PT term.

For summaries by severity/toxicity grade, a subject with multiple occurrences under the same PT or system organ class will be represented under the most severe occurrence. For summaries by relationship to study drug, a subject with multiple occurrences under the same PT or system organ class will be represented under the most related occurrence. A TEAE is considered treatment-related if its causality was related on the AE eCRF page.

The worst toxicity grade per subject, by system organ class, or per PT will be used in the CTCAE grade summary. Missing grade will be not imputed. Missing relationship to study drug will not be imputed.

An overall summary of AEs will include the number of subjects in the following categories:

- X Any TEAE
- X Any treatment-related TEAE
- X Any CTCAE Grade 3 and Grade 4 TEAE
- X Any treatment-related CTCAE Grade 3 and Grade 4 TEAE
- X Any fatal (Grade 5) TEAE
- X Any treatment-related fatal (Grade 5) TEAE
- X Any SAE
- X Any treatment-related SAE
- X Any TEAE leading to dose interruption
- X Any treatment-related TEAE leading to dose interruption
- X Any TEAE leading to dose reduction
- X Any treatment-related TEAE leading to dose reduction
- X Any TEAE leading to discontinuation of study drug
- X Any treatment-related TEAE leading to discontinuation of study drug

TEAEs will also be summarized by system organ class, PT, treatment group and SOC type (fulvestrant vs AIs) for the following:

- X All TEAEs
- X Treatment-related TEAE
- X CTCAE Grade 3 and Grade 4 TEAEs
- X Treatment-related CTCAE Grade 3 and Grade 4 TEAEs
- X Fatal (Grade 5) TEAEs

Sponsor:	Radius		
Protocol:	RAD1901-308		
Document Version No.:	1.1 (Final)	Document Date:	10-MAY-2021

- x Treatment-related fatal (Grade 5) TEAEs
- x SAEs
- x Treatment-related SAEs
- x TEAEs leading to dose interruption
- x Treatment-related TEAEs leading to dose interruption
- x TEAEs leading to dose reduction
- x Treatment-related TEAEs leading to dose reduction
- x TEAEs leading to discontinuation of study drug
- x Any treatment-related TEAE leading to discontinuation of study drug

Summary TEAE tables described above (except SAEs) will be presented using grouped PTs as well. AE grouping will be provided in a supplementary document.

All AEs with outcome of death, all serious TEAEs and TEAEs leading to treatment discontinuation will be listed.

TEAEs will also be summarized by PT, treatment group and SOC type (fulvestrant vs AIs), by descending order of overall frequency in the elacestrant group.

A by-subject data listing of all the AEs will be provided by treatment group and SOC type (fulvestrant vs AIs). The listing will include subject, verbatim term, original PT, and system organ class, TEAE flag (yes/no), SAE flag (yes/no), the AE start and stop dates and study days, AE severity grade, relationship to study drug, actions taken, and outcome. The listing will also be provided for subjects <65 years and

i H O « o « X

In addition, summary of primary cause of death will be provided by treatment group and SOC type (fulvestrant vs AIs). A listing of all deaths will be provided, including primary cause of death.

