### 1.2.3 Other Secondary

The following secondary objectives will be assessed in ESR1-mut-nd subjects:

- x To compare PFS based on blinded IRC assessment between treatment groups
- x To compare OS between treatment groups

The following secondary objectives will be assessed in ESR1-mut subjects, ESR1-mut-nd subjects, and all subjects (ESR1-mut and ESR1-mut-nd):

- x To compare PFS based on local Investigator assessment between treatment groups
- x To compare objective response rate (ORR) based on blinded IRC assessment between treatment groups
- x To compare duration of response (DoR) based on blinded IRC assessment between treatment groups
- x To compare clinical benefit rate (CBR) based on blinded IRC assessment between treatment groups
- x To compare ORR based on local Investigator assessment between treatment groups
- x To compare DoR based on local Investigator assessment between treatment groups
- x To compare CBR based on local Investigator assessment between treatment groups

The following secondary objectives will be assessed in ESR1-mut subjects and all subjects (ESR1-mut and ESR1-mut-nd):

- x To compare the safety and tolerability between treatment groups
- x To assess the pharmacokinetics (PK) of elacestrant
- x To describe the changes in Patient Reported Outcomes (PROs) and Health-Related Quality of Life (HRQOL) and the changes in PROs/HRQOL between treatment groups

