## 4 STATISTICAL METHODS

### 4.1 Sample Size Justification

Note: This section describes the justification for the sample size used when the study was initiated and was based on PFS only. This amendment adds a truncated Hochberg procedure to allow testing of the key secondary endpoint of OS while maintaining the family-wise type I error rate at 5% (2-sided). At the time of this amendment, the study is fully enrolled (N=478) and the sample size will not be increased. Section 4.2.6 describes the testing procedures to be used for OS and the power associated with the OS analysis based on the number of OS events expected for the 478 subjects.

Among the ESR1-mut subjects, the study requires approximately 160 PFS events to have a power of 80% to detect a hazard ratio of 0.610 at the 2-sided alpha level of 2.5%. Assuming a median PFS of 5.3 months for the SOC treatment group, this treatment effect represents a median PFS of 8.7 months for the elacestrant treatment group, an increase of approximately 3.4 months among the ESR1-mut subjects.

Among all subjects (ESR1-mut and ESR1-mut-nd), a total of approximately 340 PFS events will have 92% power to detect a hazard ratio of 0.667 at the 2-sided alpha level of 2.5%.

The 2-sided alpha level of 2.5% for the sample size calculation is selected to ensure that at least 1 of the 2 primary efficacy endpoints will pass the Hochberg procedure ([Hochberg, 1988](#)) to control the overall alpha level at 5.0% (see Section 4.2.6).

The study will need to randomize approximately 220 ESR1-mut subjects (110/treatment group) and a total of approximately 466 subjects of both types (ESR1-mut and ESR1-mut-nd, 233/treatment group) in a 1:1 ratio to the two treatment groups.

To prevent exceeding the target recruitment by more than 10% (i.e., 512 subjects total), if a total of 292 ESR1-mut-nd subjects is reached before 220 ESR1-mut subjects are enrolled, further enrollment will be restricted to ESR1-mut subjects only until the target of 220 is achieved.

Final analysis of the primary endpoint will be performed at approximately 160 PFS events among the ESR1-mut subjects and 340 PFS events among all subjects (ESR1-mut and ESR1-mut-nd), estimated to occur at 30-33 months after the first subject is randomized.

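### Adverse events are compared only by crude subject incidence over a window that depends on time on treatment; exposure-adjusted and time-to-first-event summaries should be added beside it

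*SAP*

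**What the plan says.** SAP 4.12.2 fixes the measure: "Adverse events will be summarized by subject incidence rates; therefore, in any tabulation, a subject contributes only once". The overall summary lists 14 categories as numbers of subjects. The tables by system organ class and preferred term follow the same pattern, by arm and by standard-of-care type. Events qualify from first dose up to a point "within 30 days of the last dose of study drug".

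SAP 1.2.3 lists among the other secondary objectives: "To compare the safety and tolerability between treatment groups". Under SAP 4.12, "safety analyses will be conducted using the Safety population for ESR1-mut subjects and all subjects".

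Duration on treatment, number of doses, dose intensity and compliance are tabulated separately (SAP 4.12.1) and are not used in the adverse event tables. Neither document plans an event rate per person-time, a time-to-first-event analysis or a fixed-window incidence. No test of adverse event frequencies is specified.

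Treatment continues to progression unless stopped earlier for an adverse event, noncompliance, a long interruption, the subject's best interest or refusal (protocol synopsis and 5.3.1). For ESR1-mut subjects, SAP 4.1 reads: "Assuming a median PFS of 5.3 months for the SOC treatment group, this treatment effect represents a median PFS of 8.7 months". For all subjects, "a total of approximately 340 PFS events will have 92% power to detect a hazard ratio of 0.667", and no medians are given.

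**The concern.** A crude percentage mixes two things: how often events arise per unit of time, and how long subjects are watched. Here the watching time ends 30 days after last dose, and last dose is usually set by progression. The trial is powered to find a difference in progression. If it finds one, the arms are likely to have been observed for different lengths of time, and two drugs with the same event hazard can show different percentages.

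What is at stake is how the between-arm safety comparison is read. The exposure tables would reveal an imbalance in duration. They would not let a reader correct the figure for a given preferred term, because that needs each subject's time to first event.

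**Working it through.** **Inputs from the documents**
- ESR1-mut: medians 5.3 and 8.7 months, hazard ratio 0.610, 160 events, 80% power, two-sided alpha 2.5% (SAP 4.1).
- All subjects: hazard ratio 0.667, 340 events, 92% power (SAP 4.1).
- Post-dose window of 30 days: w = 30/30.4375 = 0.99 months (SAP 4.12.2).
- Expected time on elacestrant about 4 months, from a 3.8-month median in Study RAD1901-005 (protocol synopsis and 5.3.1). There is no standard-of-care (SOC) counterpart.

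**Assumptions**
- Time on treatment is exponential and, in the design scenarios, tracks PFS.
- The event hazard is constant and equal in both arms.
- SOC incidences of 10% to 80% are illustrative.
- The SOC median for all subjects is taken as 5.3 months.

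**1. The plan's own figures.** 5.3/0.610 = 8.69 months, matching 8.7. By the Schoenfeld formula, z = (√160/2) × |ln 0.610| − 2.241 = 0.885, giving 81% power against the stated 80%. For 340 events and 0.667, z = 1.492, giving 93% against 92%. The design inputs are reproduced closely enough to use.

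**2. Time under observation.** The ratio of medians is 8.7/5.3 = 1.64 for ESR1-mut and 1/0.667 = 1.50 for all subjects. Mean observation time is median/ln 2 + w.
- ESR1-mut: 8.63 months on SOC, 13.54 on elacestrant, ratio 1.57.
- All subjects: 8.63 and 12.45 months (elacestrant median 5.3/0.667 = 7.95), ratio 1.44.
- If elacestrant is instead 4 months and SOC is shorter by the same ratios: 6.76/4.50 = 1.50 and 6.76/4.83 = 1.40.

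**3. Crude incidence under equal hazards.** With g = ln 2/median and event hazard h,

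P(event) = 1 − [g/(g + h)] × exp(−h × w).

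Example, ESR1-mut: SOC g = 0.1308, and an incidence of 20% gives h = 0.0282 per month. On elacestrant g = 0.0797, so P = 1 − 0.7385 × 0.9726 = 28.2%.

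| Assumed SOC incidence | Elacestrant, ESR1-mut (5.3 vs 8.7) | Elacestrant, all subjects (5.3 vs 7.95) | Elacestrant at 4.0, SOC at 5.3 |
|---|---|---|---|
| 10% | 14.8% | 13.8% | 8.0% |
| 20% | 28.2% | 26.5% | 16.4% |
| 30% | 40.2% | 38.2% | 25.1% |
| 50% | 61.1% | 59.1% | 43.9% |
| 80% | 86.3% | 85.3% | 75.7% |

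In the ESR1-mut column the gap is about 5 to 11 points. In the last column the sign changes.

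**4. Early-onset events.** The window guarantees every treated subject at least 30 days of observation, deaths aside. For events confined to that period, crude incidence is not distorted by exposure.

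**5. The person-time rate in the same case.** Suppose an identical 30% risk in both arms, all in month 1, with mean onset at 0.5 months.
- SOC: 0.30/(0.30 × 0.5 + 0.70 × 8.63) = 0.30/6.19 = 0.0485 per month.
- Elacestrant: 0.30/(0.30 × 0.5 + 0.70 × 13.54) = 0.30/9.63 = 0.0312 per month.

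The rate ratio is 0.64 with no true difference, so the person-time rate has its own bias, in the other direction.

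**The case against.** A reader might infer that the plan expects elacestrant subjects to stay on treatment about 60% longer, so that equal hazards will look like excess toxicity. The documents do not support that. The 8.7 and 5.3 months are median PFS under the ESR1-mut design alternative, not treatment durations, and for all subjects the implied figure is about 50%. The only duration stated is about 4 months on elacestrant, with no SOC figure beside it. Treatment also stops for reasons other than progression.

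Constant hazard is also doubtful for some of the drug's known events. In Study RAD1901-004, with 7 days of dosing, nausea was 43% on elacestrant vs 25% on placebo, dyspepsia 36% vs 13% and vomiting 32% vs 0% (protocol 2.2.2.2). Events of that kind can arise early, where crude incidence is sound and a person-time rate is not. Finally, the tables are descriptive, exposure is shown by arm, and no safety decision rule depends on them.

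Most of this stands, and it limits the point to a possible distortion of unknown direction. Two parts carry less weight. The reversal in the last column pairs a Phase 1 elacestrant duration with a Phase 3 design PFS for SOC. In that Phase 1 study, median duration at 400 mg (3.8 months) was not far below median PFS (4.5 months), so treatment time may well follow PFS. And if elacestrant exposure did prove shorter, crude incidence would understate its toxicity, which is equally a reason to show an adjusted measure.

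**Conclusion.** The gap is real and minor: the only planned adverse event comparison is crude incidence over a treatment-dependent window, with nothing that accounts for time at risk. If treatment tracks PFS and the design alternatives hold, mean observation time would be about 1.57 times as long on elacestrant in ESR1-mut subjects and 1.44 times in all subjects (SOC median of 5.3 months assumed for the latter). Equal constant hazards could then give, for example, 20% against about 28%.

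That size rests on three assumptions: treatment time follows PFS, hazards are constant, and the SOC incidence is as chosen. The distortion is absent for events confined to the first 30 days, smaller for very common events, and reversed if elacestrant exposure is shorter. The documents do not settle which case applies, so they support neither a predicted direction nor a claim that the safety comparison will be biased against elacestrant. They do support adding measures that help whichever way exposure differs.

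**What to change.** Keep the crude tables. For the overall adverse event summary, SAEs, Grade 3-4 TEAEs, TEAEs leading to discontinuation and the most common preferred terms, add beside them, by arm:

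- (a) subjects with a first event per 100 person-years at risk, with time at risk ending at the first event or at the close of the TEAE window;
- (b) time to first event, shown as cumulative incidence, which needs no constant-hazard assumption. Event-free subjects should be censored when their window closes; treating the end of treatment as a competing event would largely reproduce the crude figure.

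State in SAP 4.12.2 that crude incidence, (a) and (b) are read together, and that the between-arm comparison does not rest on person-time rates alone.

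The cost is a few extra tables and plots from event and dosing dates already collected. The downsides are the constant-hazard assumption behind (a) and, for (b), the assumption that censoring at the close of the window is unrelated to event risk.
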